5.6 Criteria for Removal From Study

At the one year time point the patient will complete the study. If progression of disease is noted at any time, the patient will be taken off study and at the physician's discretion, the LIUD may be removed and the patient will be treated with either definitive surgical therapy or an alternative progesterone agent. In the case of G1 EEC, progression will be defined as the presence of grade 2 endometrioid cancer or worse on the endometrial biopsy. In the case of CAH, progression will be defined as G1 EEC or worse on the endometrial biopsy. The patient will also be removed from the study and offered alternative therapies if unacceptable toxicity or complications occur due to the LIUD.

5.7 Study Completion

The patients that complete of one year of therapy will be offered continuation of the LIUD, hysterectomy, or alternative progesterone therapy. If they choose to continue LIUD treatment, they will be referred to their primary gynecologic oncologist for continued management and follow-up. The LIUD may remain in situ for five years. If they choose to have the LIUD removed they will be referred back to their primary gynecologic oncologist to discuss further options and management.

A molecular profile will be performed on the uterine specimen of any protocol patients that

undergo hysterectomy for progressive disease or at the completion of therapy. This profile is including, but not limited to, determination of expression of estrogen-induced genes and expression of PTEN and phosphorylated S6 protein by IHC. Current and future patients from MD Anderson Cancer Center and Harris Health System (Lyndon B. Johnson General Hospital) will be consented for this optional tissue collection. For MD Anderson patients who are no longer on study, we will ask for a waiver of consent to collect retrospective tissue as it may be difficult to locate these patients or they may be deceased and this tissue collection will pose minimal risk to the patients. We will use previously signed consent from the IRB approved Gyn Onc Tumor Bank protocol (LAB02-188) or the MD Anderson front door consent protocol (Lab03-0320)

5.8 Long-term Follow-up

All patients will be followed for 5 years from their last study-specific intervention, unless consent is withdrawn or the patient is lost to follow-up. No clinic visits or other patient contact is required for follow-up. Patient survival, disease status, and fertility outcomes will be followed annually through review of their medical record.

5.9 Patient Flow Diagram

Please see Appendix H for Patient Flow Diagram.

6.0 Correlative Studies

6.1 Gene Expression

6.1.1 Collection of Sample

6.1.1.1 Dilation and Curettage

This sample will be collected in the operating room. Upon collection, the specimen will be formalin-fixed and taken to the laboratory at room temperature.

6.1.1.2 Three-Month Endometrial Biopsy

This sample will be collected in the clinic room using the Pipelle collection device. Adequate tissue amount will be determined by the clinician and research coordinator collecting the specimen. Upon collection, the specimen will be formalin-fixed and taken to the laboratory at room temperature.

6.1.2 Handling of Sample

6.1.2.1 Dilation and Curettage and Three-Month Endometrial Biopsy

A hematoxylin and eosin slide will be prepared for the gynecologic pathologist to read and obtain diagnosis. The remainder of the tissue will be divided for PCR and IHC. RNA extraction will be performed on the tissue and the resultant RNA will be stored in the -80°C refrigerator until analysis.

6.2 Immunohistochemistry

6.2.1 Collection of the Sample

6.2.1.1 Dilation and Curettage

This sample will be collected in the operating room. Upon collection, the specimen will be formalin-fixed, processed by the pathologist, and taken to the laboratory at room temperature.

6.2.1.2 Three-Month Endometrial Biopsy

These samples will be collected in the clinic room. Adequate tissue amount will be determined by the clinician and research coordinator collecting the specimen. Upon collection, the specimen will be formalin-fixed, processed by the pathologist, and taken to the laboratory at room temperature.

6.2.2 Handling of Sample

6.1.2.1 Dilation and Curettage and Three-Month Endometrial Biopsy

A hematoxylin and eosin slide will be prepared for the gynecologic pathologist to read and obtain diagnosis. The remainder of the tissue will be divided for PCR and IHC. Four slides will be cut from the formalin-fixed, paraffin-embedded tissue for performance of immunohistochemistry.

6.2.3 Scoring of IHC Results

6.2.3.1 PTEN

Loss of PTEN expression will be defined as no staining in greater than 10% of the endometrial glands in the specimen[20].

6.2.3.2 Phosphorylated mTOR

Positive expression of phosphorylated mTOR will be defined as moderate (2+) to strong (3+) staining in greater than 20% of the endometrial glands in the specimen[20].

7.0 Statistical Considerations

7.1 Sample Size Calculation

A Bayesian Phase II design was employed for sample size calculation. We will enroll and evaluate a minimum of 20 evaluable (those who complete 12 months of therapy) patients and a maximum of 50 evaluable patients in this study.

7.3 Endpoints

The primary outcome will be response to therapy, which is defined as complete response or partial response (detailed in section 5.5), assessed at the one year endometrial biopsy. Secondary outcomes will include toxicity and complication information. The molecular profile will be utilized to determine if response to therapy can be predicted. Additionally, toxicity assessment and quality of life assessment with the SF-36 survey will be performed at baseline and at each 3-month follow up visit as described in Section 5.4.

7.4 Analysis of primary outcome

Once we have completed the study, we will estimate the treatment success rate with a 90% credible interval. For example, if 27 of 50 patients (54%) have complete remission, the 90% credible interval for the treatment success rate will be 43.1% to 65.6%. If 35 of 50 patients (70%) have complete remission, the 90% credible interval for the treatment success rate will be 59.0% to 79.7%.

If the upper bound of the 90% credible interval is less than our goal of 65% success rate, we will not pursue further study of this intervention.

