1.0 Objectives

1.1 Primary Objective

- 1.1.1 To determine the efficacy of the Levonorgestrel Intrauterine Device (IUD) to treat complex atypical hyperplasia (CAH) and grade 1 endometrioid endometrial carcinoma (G1 EEC).
- 1.1.2 To determine if response to therapy can be predicted based on the molecular profile of the tumor or by change in gene expression after therapy.

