2.2 Rationale

One of the most well-established risk factors for the development of CAH and endometrial

carcinoma is exposure to unopposed estrogen. In fact, a majority of the key conditions associated with endometrial cancer are directly or indirectly related to estrogen. Progesterone is known to counteract the effects of estrogen in the endometrium, thus, it has been used as a primary therapy for CAH and as an alternative primary therapy or adjuvant therapy for endometrial cancer[2].

Progesterone has been demonstrated to be an acceptable and efficacious option for treatment of complex atypical hyperplasia and grade 1 endometrioid endometrial carcinoma[3,7]. Despite the success of progesterone treatment, many women do not tolerate the side effects of systemic progesterone or are unable to maintain compliance with this therapy[8]. Montz et al evaluated the use of a progesterone releasing intrauterine device (Progestesert) to treat stage 1a, grade 1 endometrioid endometrial carcinoma. They demonstrated complete regression of G1EEC in 7 of 11 patients at 6 months and in 6 of 8 patients at 12 months[9]. Unfortunately, this therapy is no longer available for therapeutic use. The Levonorgestrel Intrauterine Device (LIUD) has been demonstrated to provide a consistent dose of progesterone to the uterine cavity with minimal systemic effects[10]. The toxicity of this treatment is low, with the most common complications consisting of irregular bleeding, expulsion, or uterine perforation during placement[11].

The studies of the LIUD for complex atypical endometrial hyperplasia are promising, but have been limited by low numbers. In a study of endometrial hyperplasia, there was regression of disease in 100% patients (n=26) treated with the LIUD compared to only 55% of patients treated with oral progesterone. It is important to note that only two of the patients in this study had CAH[12]. Wildemeersch et al noted 100% regression after Mirena placement in the eight patients with complex atypical hyperplasia in their study[13].

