The use of the Mirena for the treatment of grade 1 endometrioid endometrial carcinoma has been less well studied, with only a few cases documented in the literature. Giannopoulos et al reported complete regression of a well-differentiated endometrial carcinoma after treatment with the LIUD[14]. Other case series, however, have had lower rates of success. Bahamontes et al treated two women with morbid obesity and G1EEC with the Mirena while awaiting gastroplasty for weight reduction. Both women had residual G1EEC in their hysterectomy specimens after 6 and 7 months, respectively[15,16]. In a case series of four women with G1EEC treated with LIUD, only one woman had complete regression at 6 months[16]. A larger study is necessary to clarify if the LIUD is effective in the treatment of grade 1 endometrioid endometrial carcinoma.

Given the success of oral progesterone for the treatment of both conditions, the LIUD is a rational option for patients with CAH and grade 1 endometrioid endometrial carcinoma. However, the existing literature is conflicting regarding the success of this treatment. Therefore, we propose a phase II trial to assess the efficacy of the LIUD for treatment of complex atypical hyperplasia or Grade 1 endometrioid carcinoma. Patients will receive this treatment for one year, as the median time to complete regression of G1 EEC during oral progesterone therapy is generally 12 weeks, with a range of 4 – 60 weeks[3].

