5.3 Pretreatment Evaluation

After signing the informed consent, the patients will follow one of two treatment plans depending on their initial biopsy diagnosis. All patients will undergo a urine pregnancy test (women of child bearing potential) and cervical cultures in clinic to rule out pregnancy and active cervical infection. Patients with G1 EEC will undergo clinical staging procedures including chest radiography and MRI of the abdomen and pelvis. This will be a routine MRI of the abdomen and pelvis with standard pulse sequences including dynamic gadolinium enhanced imaging of the uterus.

Women who are unable to undergo MRI due to morbid obesity or other contraindication will have a CT scan of the abdomen and pelvis and transvaginal ultrasound. For those patients who are unable to undergo CT due to morbid obesity, transvaginal ultrasound will be performed. Scans will be reviewed by the diagnostic radiology collaborator on the study. Women will be excluded if there is evidence of extrauterine spread of disease.

Both cohorts of patients (CAH and G1 EEC) will then undergo an exam under anesthesia (EUA) and a dilation and curettage (D&C) in the operating room to sample the entire endometrium. This specimen will be read by a certified gynecologic pathologist at our institution and report dictated in the electronic medical record. At the time of D&C, the LIUD will be placed. Women who have previously undergone D&C for this diagnosis will not be required to undergo a second D&C. The pathology specimen will be obtained for review and confirmation of diagnosis and for the correlative studies to be performed. The LIUD will then be placed in the clinic setting.

If patients with an initial diagnosis of CAH are upgraded to G1 EEC, they will be assessed for eligibility through inclusion criteria 1. If the patient does not meet inclusion criteria, they will be removed from the study. Otherwise, they will undergo chest radiography, and MRI of the abdomen and pelvis and/or CT of the abdomen and pelvis and/or transvaginal ultrasound as detailed above in the post-operative period. Women will remain on study if they have confirmed CAH and/or G1 EEC on the D&C specimen and have no evidence of extrauterine spread of disease. If a woman is excluded from the trial after LIUD is placed, the LIUD will be subsequently removed. Removal of the LIUD can be performed in the operating room if the patient proceeds with surgical treatment or in the clinic.

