5.5 Criterion for Response

Response is defined as follows:

Complete response is defined as no endometrial abnormality or the presence of endometrial hyperplasia without cytologic atypia at the one year time point.

Partial response is defined as the presence of complex endometrial hyperplasia with cytologic atypia in patients with an initial diagnosis of grade 1 endometrial cancer, at the one year time point.

Stable disease is defined as no change in diagnosis at the one year time point.

Progressive disease is the presence of grade 2 cancer or above in patients with an initial diagnosis of grade 1 cancer OR presence of grade 1 cancer or above in patients with an initial diagnosis of complex atypical hyperplasia at any time point.

Patients with stable disease or progressive disease will be categorized as non-responders for the purposes of molecular analysis.

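### Section 7.4 plans one pooled success rate for CAH and G1 EEC with an uncontrolled mix, so the trial may not answer objective 1.1.1 for either disease

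*Combined protocol and SAP*

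**What the plan says.** Objective 1.1.1 is to determine LIUD efficacy in CAH and in G1 EEC. Section 2.2 says where evidence is lacking: "A larger study is necessary to clarify if the LIUD is effective in the treatment of grade 1 endometrioid endometrial carcinoma".

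The analysis plan does not separate the two. Section 7.2 has one Beta(1.3, 0.7) prior and one boundary. Section 7.4 states that "we will estimate the treatment success rate with a 90% credible interval", with one 65% goal and one decision: no further study if the upper bound is below 65%. Section 7.5 has no efficacy estimate by diagnosis. Sections 5.1 and 7.1 set only a total of 20 to 50 evaluable patients, with no quota, cap or minimum per disease. Entry differs too: any CAH qualifies, but G1 EEC only with a fertility wish, BMI above 40 or ASA class 3 or 4.

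Two definitions also depend on diagnosis. Section 7.3 counts partial response as success, and 5.5 allows partial response only in G1 EEC. Section 5.5 then scores against the initial diagnosis; progression includes "presence of grade 1 cancer or above in patients with an initial diagnosis of complex atypical hyperplasia at any time point". Section 5.3 uses that term for the biopsy before D&C: "If patients with an initial diagnosis of CAH are upgraded to G1 EEC, they will be assessed for eligibility". Those who remain eligible stay on study.

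**The concern.** A pooled rate is a weighted average, and here referral sets the weights. If the two diseases respond alike, that does no harm. If they do not, the same drug effects can end in a futility stop or in a completed trial, depending on the mix. The only stated decision is a no-go, so a pooled result that avoids it says little about carcinoma, which is where the protocol says evidence is needed.

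The protocol's own background makes a difference plausible without establishing it. For CAH, one report "noted 100% regression after Mirena placement in the eight patients with complex atypical hyperplasia in their study", and both CAH patients in another LIUD study regressed. For G1 EEC treated with the LIUD there is one single-patient success, two failures, and a third report: "In a case series of four women with G1EEC treated with LIUD, only one woman had complete regression at 6 months". Against this, a different device, the progesterone IUD, gave "complete regression of G1EEC in 7 of 11 patients at 6 months and in 6 of 8 patients at 12 months".

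The baseline wording is a smaller, linked matter. Any split by disease needs a rule for a woman whose biopsy shows CAH and whose D&C shows G1 EEC. Read literally, 5.5 calls her unchanged carcinoma progressive disease, and 5.6 would take her off study at the first follow-up biopsy. CAH at one year would be stable disease rather than partial response.

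**Working it through.** **1. Reproduce the plan's figures.** With x successes in n, the posterior is Beta(1.3 + x, 0.7 + n - x), and the 90% interval runs from its 5% to its 95% quantile.

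- 27/50: Beta(28.3, 23.7) gives 43.1-65.6%, as in 7.4.
- 35/50: Beta(36.3, 15.7) gives 59.0-79.7%, as in 7.4.
- Boundary: the largest x with Pr(rate ≥ 65% | data) < 0.05 reproduces all 18 points in 7.2, from 9/20 to 26/49.
- Early stopping, by exact binomial recursion over that boundary with a check after every patient from 20 to 49: 0.799 at a true rate of 50% (Table 1: 0.793) and 0.132 at 65% (Table 1: 0.133).

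The arithmetic of the plan is sound. The question is what it estimates.

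**2. Background rates.** LIUD in CAH: 8/8 + 2/2 = 10/10. LIUD in G1 EEC: 1/1 + 0/2 + 1/4 = 2/7, with the failures in the two series read at about 6 to 7 months. Progesterone IUD in G1 EEC: 7/11 at 6 months and 6/8 at 12 months.

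**3. Effect of the mix.** The documents give no expected mix and no rate by disease, so these are assumptions. Let m be the CAH share, 90% the true CAH success rate and q the true G1 EEC rate. The pooled rate is p = 0.9m + q(1 - m). For example, m = 0.3 and q = 0.3 give 0.27 + 0.21 = 0.48. Probability that the rule in 7.2 stops the trial:

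| CAH share | q = 30%: p | stop | q = 50%: p | stop |
|---|---|---|---|---|
| 30% | 0.48 | 86.5% | 0.62 | 23% |
| 40% | 0.54 | 62% | 0.66 | 11% |
| 50% | 0.60 | 32% | 0.70 | 4% |
| 60% | 0.66 | 11% | 0.74 | 1% |
| 70% | 0.72 | 2% | 0.78 | 0.2% |

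With q = 70%, stopping is at most 0.5%, which is correct because both rates exceed 65%.

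The final rule in 7.4 adds nothing to these probabilities. At n = 50 it needs 26 or fewer successes (26/50 has upper bound 63.7%, 27/50 has 65.6%), and a trial with 26 or fewer at 49 has already stopped.

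**4. What a pooled result can hide.** An illustrative split of 33/50:

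| Group | Result | Posterior | 90% interval |
|---|---|---|---|
| Pooled | 33/50 | Beta(34.3, 17.7) | 54.9-76.3% |
| CAH | 27/30 | Beta(28.3, 3.7) | 78.1-96.0% |
| G1 EEC | 6/20 | Beta(7.3, 14.7) | 17.9-50.2% |

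The pooled result does not meet the no-go, while the G1 EEC interval lies wholly below 65%.

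**5. Would a split be informative?** The G1 EEC upper bound is below 65% with at most 3 successes in 10, or at most 9 in 20. Binomial probability of that:

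| True G1 EEC rate | n = 10 | n = 20 |
|---|---|---|
| 30% | 65% | 95% |
| 50% | 17% | 41% |

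**6. Baseline scoring.** The documents give no rate of upgrade at D&C, so the number of women affected is unknown. Each partial response scored as stable disease moves a 50-patient rate by 1/50 = 2 points.

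**The case against.** Pooling was a reasoned choice. Section 2.1 argues that the diseases are closely related and hard to tell apart: 42% concurrent carcinoma after a CAH biopsy, and 38% agreement with an initial CAH diagnosis. Objective 1.1.1 can be read as joint efficacy. That supports enrolling both diseases and keeping a pooled primary analysis. It does not say the rates are equal, and it gives no reason against estimates by disease. It does mean that the subgroup labels will carry some misclassification, which D&C confirmation reduces but does not remove.

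The 30% scenario is pessimistic. The 2/7 counts complete regressions, with the series failures read at about 6 to 7 months. Success under 7.3 includes partial response and is read at one year, and 5.5 lets complete response include hyperplasia without atypia. Protocol-defined success in G1 EEC could be well above 30%. This stands as a limit on size, and it is why the 50% and 70% cases matter.

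The fix is also modest. Small groups give wide intervals, the mix stays uncontrolled, and a breakdown could be reported without being planned. All true, but planning it settles the grouping and the prior before results are seen.

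On baseline scoring, 5.3 restages an upgraded woman as G1 EEC, 5.6 does not use the word initial, and section 8.0 leaves response-based removals to the study chairman and pathologist. Automatic removal is therefore unlikely in practice. The wording of 5.5 still says otherwise, and 5.6 does not state which specimen defines the case. The 2-point figure does not cover women removed as progressive, who may leave the denominator because 7.1 defines evaluable as completing 12 months.

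**Conclusion.** The concern holds. The plan names two diseases and an open question about one of them, then provides a single pooled estimate with nothing by diagnosis. Masking needs a low G1 EEC rate and a substantial CAH share. With 90% and 30% assumed, the chance of a futility stop falls from 86.5% to 2% as the CAH share rises from 30% to 70%. With 90% and 50%, it falls from 23% to 0.2%. With G1 EEC at 70% nothing is masked, and a split would simply show that.

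These figures assume constant true rates, a CAH share that applies independently to each patient, and monitoring after every patient. The change should be made. Confidence in its practical size is medium, because neither the mix nor the rates by disease are known. The baseline wording is a real ambiguity of unknown frequency.

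**What to change.** Keep the pooled primary analysis and the rule in 7.2. Add to 7.4:

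> The success rate with a 90% credible interval (Beta(1.3, 0.7) prior) will also be reported separately for CAH and G1 EEC as supportive estimates, with the number in each group. The pooled rate alone will not be read as evidence of efficacy in either disease.

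In 5.5, and by reference in 5.6, replace the initial diagnosis with the pathologist-confirmed D&C diagnosis at or before LIUD placement, and use that diagnosis to form the two groups.

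The cost is two sentences, one wording change and one table from data already collected. The price is imprecision: half-widths are about 9 points for 27/30, 16 for 6/20 and 23 for 5/10 (29-75%), so a small group may be inconclusive. Because 7.2 stays pooled, poor results in G1 EEC could still stop CAH accrual; the split would reveal this but not prevent it.

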7.5 Analysis of secondary outcomes

A secondary aim of this study is to determine whether treatment success is related to a patient's genetic profile. To this end, we will measure PR, EIG121, IGF-I, RALDH2, sFRP1, sFRP4, and IGF-IR at baseline and again at the 3-month biopsy. Change from baseline (\bar{a}) for each biomarker will be calculated and the hypothesis that

$H_0: \bar{a} = 0$ vs. $H_1: \bar{a} \neq 0$

will be tested with a paired t-test. Because genetic profile information is highly skewed, natural log transformations will be made to the data prior to calculating change from baseline and completing the t-test. Previous data indicate that the standard deviation of the log-transformed data will be approximately 1. Table 2 shows the power of our test when we use a statistical significance level of 5%, both when the standard deviation is 1 and again if the standard deviation should be 1.25, slightly larger than we estimated. Power was assessed at sample sizes $n = 20$, 25, 30, 35, 40, 45 and 50 because our actual sample size might range anywhere between 20 and 50 patients.

Table 2. Power to Determine Changes in Genetic Profile ($\alpha = 5\%$, two-sided test, hypothesized difference of 0.5)

Sample Size	Power	
	When SD = 1	When SD = 1.25
20	56.45%	39.70%
25	66.97%	48.40%

30	75.40%	56.28%
35	81.95%	63.28%
40	86.94%	69.40%
45	90.66%	74.68%
50	93.39%	79.18%

Although we might stop the trial early, our median sample size is most likely 50, and therefore we should have at least 79% power to detect a difference of 0.5 in our genetic profile data.

Change in immunohistochemical expression will be analyzed for association with response using a chi-square analysis.

Summary statistics will be calculated for quality of life scores, both at baseline and every three months afterwards until the patient completes the study. This analysis will be descriptive.

Summary statistics will also be completed on LIUD toxicity. The LIUD toxicity profile is known to be low, and it tends to be well-tolerated, therefore we do not anticipate a need to stop the trial early due to toxicities. However, incidence of toxicities will be calculated.

We will calculate period prevalence and incidence of recurrence along with 95% confidence intervals. Period prevalence is calculated as the number of patients who recur divided by number of patients at risk for recurrence. Incidence is calculated as the number of patients who recur divided by person-time follow-up. Recurrence is defined as return to original disease state or worse after being disease-free. Finally, the proportion of patients who return to a worsening disease state after an initial response will be calculated. Specifically, it will calculate the proportion of patients who have progressive disease if their best response was stable disease, partial response, or complete response.

Summary statistics will be calculated for disease status and fertility outcomes. This analysis will be descriptive.

We will calculate period prevalence and incidence of recurrence along with 95% confidence intervals. Period prevalence is calculated as the number of patients who recur divided by number of patients at risk for recurrence. Incidence is calculated as the number of patients who recur divided by person-time follow-up. Recurrence is defined as return to original disease state or worse after being disease-free. Finally, the proportion of patients who return to a worsening disease state after an initial response will be calculated. Specifically, it will calculate the proportion of patients who have progressive disease if their best response was stable disease, partial response, or complete response.

Summary statistics will be calculated for disease status and fertility outcomes. This analysis will be descriptive.

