1.2 Secondary Objectives

- 1.2.1 To assess quality of life outcomes in patients treated with Levonorgestrel IUD.
- 1.2.2 To document the toxicity profile of the Levonorgestrel IUD in the treatment of complex atypical hyperplasia and grade 1 endometrioid endometrial cancer.
- 1.2.3 To evaluate the molecular profile of the hysterectomy specimen of patients treated with the Levonorgestrel IUD. Compare molecular profile in pretreatment tissue to hysterectomy tissue between responders and non-responders to Levonorgestrel IUD therapy.
- 1.2.4 To evaluate long-term survival, disease status, and fertility outcomes in patients with Levonorgestrel IUD.

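### Section 7.5 sets out to relate treatment success to gene expression, but its only mRNA test leaves response out, so the mRNA part of objective 1.1.2 has no analysis that can answer it

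*Combined protocol and SAP*

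**What the plan says.** Objective 1.1.2, listed in section 1.1 as primary, reads: "To determine if response to therapy can be predicted based on the molecular profile of the tumor or by change in gene expression after therapy". Section 7.5 takes this up in its opening sentence, which starts "A secondary aim of this study is to determine whether treatment success is related to" and names genetic profile as the other side of the relation. The sentence after it reads: "To this end, we will measure PR, EIG121, IGF-I, RALDH2, sFRP1, sFRP4, and IGF-IR at baseline and again at the 3-month biopsy". The hypothesis it then writes down is that the mean change from baseline is zero for each biomarker. This "will be tested with a paired t-test", and "natural log transformations will be made to the data prior to calculating change from baseline and completing the t-test".

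Table 2 gives the power of that test for a hypothesized difference of 0.5. The text concludes that "we should have at least 79% power to detect a difference of 0.5 in our genetic profile data".

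One molecular test in section 7.5 does use response: "Change in immunohistochemical expression will be analyzed for association with response using a chi-square analysis".

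Other sections show that a response-based molecular analysis was intended, but none names a method:
- Section 1.2.3 states a comparison: "Compare molecular profile in pretreatment tissue to hysterectomy tissue between responders and non-responders to Levonorgestrel IUD therapy".
- Section 5.5 classes stable and progressive disease as non-response for the molecular analysis.
- Section 7.3 defines response as complete or partial response, and says the molecular profile will be used to find out whether response can be predicted.
- Section 6.2.3 fixes the cut-offs for PTEN loss and for positive phosphorylated mTOR.

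**The concern.** A test that does not contain the outcome cannot show a relation to the outcome. Section 7.5 states an aim about treatment success and offers, as the means to it, a test of whether expression moves on average across everyone. Section 2.3 gives that test a proper purpose, namely evidence that the device acts on the endometrium. It is a different question from whether a patient's expression, or its change, tells responders from non-responders.

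If the plan is followed as written, the mRNA part of a listed objective has no pre-specified analysis. Someone would have to choose, with the data in hand, whether to use baseline expression or change, and which model to fit. A significant paired test could also be reported as if it bore on prediction.

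Baseline PTEN and phosphorylated mTOR are in a similar position. Section 2.3 justifies them as candidate predictors and their cut-offs are fixed, but the only planned test concerns their change.

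**Working it through.** **Step 1. Reproduce Table 2.** Inputs from section 7.5: difference 0.5 on the natural-log scale, SD 1 or 1.25, two-sided 5%, n = 20 to 50. The text describes the SD as that of the log-transformed data. Table 2 uses it as the SD of the within-patient change, and so do I.

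The formula is one-sample t power from the noncentral t distribution, with df = n − 1 and noncentrality = 0.5 × √n / SD. At n = 50 the noncentrality is 0.5 × 7.071 / 1 = 3.54 for SD 1, and 3.54 / 1.25 = 2.83 for SD 1.25.

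| n | SD 1 | SD 1.25 |
|---|---|---|
| 20 | 56.45% | 39.70% |
| 25 | 66.97% | 48.40% |
| 30 | 75.40% | 56.28% |
| 35 | 81.95% | 63.28% |
| 40 | 86.94% | 69.40% |
| 45 | 90.66% | 74.68% |
| 50 | 93.39% | 79.18% |

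All 14 cells match. Table 2 is therefore the power of a test of mean change in one pooled group.

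**Step 2. Match each marker to a test that uses response.**

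| Marker | Test named in 7.5 | Uses response? |
|---|---|---|
| Baseline mRNA, 7 genes | none | no |
| 3-month mRNA change, 7 genes | paired t-test against zero | no |
| Baseline PTEN, phosphorylated mTOR | none | no |
| Change in immunohistochemistry | chi-square | yes |

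**Step 3. Check the logic by simulation** (40,000 trials, n = 50, SD of change 1). The split is 33 responders to 17 non-responders, because 65% of 50 is 32.5; applying the 65% goal to this grouping is an assumption.

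- Equal fall of 0.5 in every patient, no relation to response: paired test significant 93.3% of the time, group comparison 4.8%.
- Mean change −0.34 in responders and +0.66 in non-responders, a difference of 1.0 with overall mean (33 × −0.34 + 17 × 0.66) / 50 = 0: paired test significant 3.1% of the time, group comparison 90.9%.

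The second case is built only to test the logic. Section 2.3 expects these genes to fall under treatment, so it is not a forecast.

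**Step 4. Illustrate the power of a response-based comparison.** The documents give no between-group difference. Assume the 0.5 of Table 2 lies between the two groups, paired tissue is available for all 50, 50% to 80% are responders, and one gene is tested at an unadjusted 5%. The formula is two-sample t power with df = n1 + n2 − 2 and noncentrality = 0.5 / (SD × √(1/n1 + 1/n2)).

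| Split | Noncentrality, SD 1 | Power, SD 1 | Power, SD 1.25 |
|---|---|---|---|
| 25 v 25 | 0.5 / 0.283 = 1.77 | 41.0% | 28.3% |
| 30 v 20 | 0.5 / 0.289 = 1.73 | 39.7% | 27.4% |
| 33 v 17 | 0.5 / 0.299 = 1.67 | 37.5% | 25.9% |
| 35 v 15 | 0.5 / 0.309 = 1.62 | 35.5% | 24.6% |
| 40 v 10 | 0.5 / 0.354 = 1.41 | 28.3% | 19.8% |

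The same figures apply to baseline expression if its log SD is 1 or 1.25. At 33 v 17, the difference detectable with 80% power is 0.85 (SD 1) or 1.07 (SD 1.25).

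**The case against.** The best defence is that the paired test is the right one for the pharmacodynamic question in section 2.3, that Table 2 is correct and labelled as power for changes, and that this is correlative work in a small single-arm trial. All of that stands. It does not supply the missing analysis: section 7.5 presents the paired test as serving the success-related aim, and does not call the prediction work exploratory.

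Some stronger readings are tempting, but the documents do not support them:

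- **That objective 1.1.2 has no response-linked test at all.** Change in immunohistochemistry is tested against response by chi-square. The gap is mRNA, plus baseline PTEN and phosphorylated mTOR.
- **That the plan claims 79% power for prediction.** The sentence speaks of detecting a difference in the genetic profile data, and Table 2's title refers to changes. The figure just should not be carried over.
- **That the outcome for the molecular analysis is undefined.** Sections 5.5 and 7.3 together give complete plus partial response against stable or progressive disease. Sections 7.2 and 7.4 count complete remissions, but that conflict concerns the primary endpoint and is a separate matter.
- **That power for prediction must fall below Table 2.** This depends on the assumed difference. At 33 v 17, a between-group difference of 1.1 would give 95.1% (SD 1) or 82.3% (SD 1.25). The statement holds only for the same 0.5.

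**Conclusion.** The method stated in section 7.5 is wrong for the aim it is attached to, and should be fixed. That rests on the text alone: response does not enter the mRNA test, and no other section gives an mRNA test, or a baseline PTEN or phosphorylated mTOR test, that uses it.

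The size is illustrative. For the same 0.5 difference at n = 50, Table 2's 93% (SD 1) and 79% (SD 1.25) compare with about 28% to 41% and 20% to 28% for a responder comparison. This assumes 50% to 80% responders, complete paired tissue and no multiplicity adjustment. The between-group difference and the split are my assumptions, not figures from the plan.

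A reader might infer that the efficacy conclusion is at risk. It is not, because nothing in the futility rule or the final credible-interval rule depends on this analysis.

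**What to change.** In section 7.5:

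1. Keep the paired t-test and Table 2, labelled as the pharmacodynamic analysis.
2. Add a pre-specified response-based analysis, by logistic regression or a two-group comparison, reported with intervals. Apply it to baseline log expression and, separately, to 3-month log change for each of the 7 genes, and to baseline PTEN loss and baseline phosphorylated mTOR by the section 6.2.3 cut-offs. Use the grouping from sections 5.5 and 7.3 (complete or partial response against stable or progressive disease) in place of the looser term treatment success.
3. Label this analysis exploratory, or state its power with an assumed between-group difference. Also say how the number of markers will be taken into account when the results are read. The list in item 2 is 7 + 7 + 2 = 16 tests, so at 5% each about 16 × 0.05 = 0.8 would be significant by chance if no marker were related to response.

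The cost is some SAP wording and a few extra models on data already to be collected. If power is stated for the same 0.5 difference, it will be lower than in Table 2. The sample size, the futility rule and the go/no-go rule do not change.
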